1 PROTOCOL SUMMARY

Background and Rationale

A cosmetic product that is freely available to the consumer must be safe when applied under normal or reasonably foreseeable conditions of use. Thus, as a general requirement, the safety of a developmental formulation should be confirmed before it is marketed.

Acceptability 'in-use' studies are useful clinical models with which to determine the irritation potential (local tolerance) of a cosmetic formulation to provide confidence the finished product is suitable for general sale.

The objective of this clinical study is to determine the local cutaneous and ocular tolerance of a developmental cosmetic facial serum in healthy females with sensitive facial skin under normal conditions of use.

Objectives and Endpoints

| Objective(s) | Endpoint(s) |
|--|---|
| Primary | |
| To determine the local cutaneous tolerance profile of the investigational product in healthy females with sensitive facial skin under normal conditions of use. | Change from baseline (prior to any product application) in dermatologist visual assessment scores of signs and symptoms of cutaneous irritation to 21 (+2) days of product use. |
| Secondary | |
| To determine the local ocular tolerance profile of the investigational product in healthy females with sensitive facial skin under normal conditions of use. | Change from baseline (prior to any product application) in ophthalmologist visual assessment scores of signs and symptoms of ocular irritation to 21 (+2) days of product use. |
| To determine the local cutaneous and ocular tolerance of the investigational product from the perspective of the subject in healthy females with sensitive facial skin under normal conditions of use. | Change from baseline in subject self-assessment scores of signs and symptoms of cutaneous and ocular irritation to 1-2 hours after first product application and following 21 (+2) days of use. |
| Safety | |
| To evaluate the general safety of two cosmetic facial serums. | Frequency and severity of Adverse Events. |

Study Design

This is a randomized, evaluator-blind (dermatologist and ophthalmologist), 2-arm, parallel-group, single-center, non-comparative clinical 'in-use' study to determine the local cutaneous and ocular tolerance of a developmental cosmetic facial serum formulation in healthy female subjects aged 18 to 65 years (inclusive) with clinically evaluated sensitive skin, as determined by a positive response to a Lactic Acid Sting Test (LAST), with minimal signs or symptoms of cutaneous irritation and no signs or symptoms of ocular irritation. A reference product, proven to be suitable for use in a sensitive skin population, is included to enable the study to be conducted in a randomized and blinded manner, rather than as a single-arm or open-label study, to minimize bias and ensure a robust outcome.

A sufficient number of subjects will be screened (approximately 180) to randomize 90 subjects to ensure that at least 60 subjects (30 per arm) complete the study.

At Visit 1 (screening), subjects who agree to participate in the study by signing the informed consent will be assessed by a qualified dermatologist for baseline clinical assessments of the signs and symptoms of cutaneous irritation and by a qualified ophthalmologist for baseline clinical assessments of the signs and symptoms of ocular irritation. Following these assessments, a LAST will be conducted in the nasolabial region to confirm whether the subject has sensitive skin. Subjects will only be considered eligible to continue in the study if they present a positive response to the LAST. Medical history, Fitzpatrick skin type, prior, current and concomitant medication will also be recorded at this visit. Subjects will be asked to self-assess baseline signs and symptoms of cutaneous and ocular irritation prior to the LAST and any product application.

Subjects will only be considered eligible to continue in the study if they have a dermatologist signs and symptoms cutaneous irritation score of greater than or equal to 0.5 (very slight) for erythema and a score of greater than or equal to 0.5 (very slight) for dryness, a score of 0 (none) or 0.5 (very slight) for scaling and 0 (none) or 0.5 (very slight) for edema. Any subject with a score of 3 (severe) in any cutaneous irritation attribute will exclude the subject from the study, as this does not reflect the target population for the product. Any ophthalmologist signs and symptoms attribute score of greater than 0 (none) will exclude the subject from the study.

For subjects who continue to be eligible to participate in the study, the first application of their assigned product will be at the investigational site, under the supervision of a trained technician. Subjects will be asked to complete further self-assessment questions of the signs and symptoms of cutaneous and ocular irritation they are experiencing, 1-2 hours after first application. Subjects will then be instructed to apply their assigned product at home again the same evening and twice-daily for 21 (+2) days as part of their normal skin care routine. A paper diary will be provided to each subject to record the number of daily applications of product, from first application at site to final application at home. The final application of product will be at home on the morning of the final visit (Visit 2).

At Visit 2 (final visit), the dermatologist and ophthalmologist will conduct final clinical assessments of the signs and symptoms of cutaneous and ocular irritation, respectively. Subjects will also be asked to conduct a final self-assessment of the signs and symptoms of cutaneous and ocular irritation. Subjects will return their completed diary and supplied product and will subsequently be discharged from the study.

Study Products

Subjects will be assigned to 1 of the 2 study products in accordance with the randomization schedule.

The investigational product is a developmental formulation intended to be used as a cosmetic facial serum by adult consumers with sensitive facial skin. The comparator product is a commercially marketed facial serum, also intended to be used by adult consumers with sensitive facial skin.

The instructions for use provided to subjects in this study are consistent with those intended to be communicated to consumers when the product is made freely available for purchase.

Type and Planned Number of Subjects

Healthy female subjects, aged 18 to 65 years with clinically assessed sensitive skin, and no ophthalmological conditions will be enrolled into this study. Female subjects with sensitive skin have been selected as they are the target consumers for the finished product with greater familiarization and habitual use of facial products.

A sufficient number of subjects will be screened (approximately 180) to randomize 90 subjects to ensure that at least 60 subjects (30 per arm) complete the study. It is deemed that 30 subjects per arm are considered sufficient to assess the primary endpoint: dermatologist assessment of signs and symptoms of cutaneous irritation total score. The sample size for this study has been selected based on clinical considerations and to ensure compliance with the Agência Nacional de Vigilância Sanitária (ANVISA) Guideline for the Safety Evaluation of Cosmetic Products (ANVISA, 2012) which mandates an investigational product be tested on at least 30 subjects.

Schedule of Activities

The schedule of activities table provides an overview of the subject visits and study procedures.

The investigator may schedule visits (unplanned visits) in addition to those listed on the schedule of activities, in order to conduct evaluations or assessments required to protect the well-being of the subject.

Table 1-1 Schedule of Activities

| Procedure/Assessment | Screening/Baseline | Final Visit |
|--|--------------------|-------------------------|
| | Visit 1 Day 1 | Visit 2 Day 21 (+ 2) |
| Informed Consent (date and time captured) | X | |
| Demographics | X | |
| Medical History | X | |
| Medications Review | X | X |
| Inclusion/Exclusion Criteria | X | |
| Fitzpatrick Skin Type Assessment | X | |
| Subject Self-Assessment | X ^a | X |
| Clinical Assessment by Dermatologist | X | X |
| Clinical Assessment by Ophthalmologist | X | X |
| Lactic Acid Sting Test (LAST) | X | |
| Subject Eligibility for Enrollment | X | |
| Randomization | X | |
| Product and Diary Dispensing | X | |
| Supervised Product Application ^b | X | |
| Adverse Events (AEs) Review ^c | X | X |
| Product and Diary Return | X | X |
| Study Conclusion/Subject Exit from Study | | X |

a. Subject self-assessment on Visit 1 will occur twice; once prior to the LAST and product application and once 1-2 hours after first supervised product application.

b. Supervised product application should not occur until at least 30 minutes following the LAST.

c. Adverse Events (AEs) and therefore all Serious Adverse Events (SAEs) will be collected immediately after a subject provides consent to participate in the study by completing the Informed Consent Form (ICF).

Footnotes:

The diary will be used to maintain and record compliance and to capture subject comments.

The diary will be reviewed by the Investigator or their designee at final visit.

First product application will be conducted at the site under the supervision of the investigator or their designee.

2 INTRODUCTION

In recent years the cosmetic industry has grown considerably, along with its concern for developing safe and effective products. Heightened industry awareness, consumer and regulatory agency requirements have led cosmetic manufacturers to adopt procedures that provide a robust assessment of the risks and benefits of their products. This includes the conduct of clinical tests to assess safety and efficacy, which are often coordinated by dermatologists or other experts before marketing a new product. These procedures provide greater assurance of safety for cosmetic manufacturers, increasing their credibility and confidence among consumers.

A cosmetic product on the market must not cause damage to human health when applied under normal or reasonably foreseeable conditions of use, taking into account, in particular, the product's presentation, its labelling, and any instructions. (Cosmetics Europe, 2004)

Skin contact with topical products such as cosmetics may trigger different types of reactions including eczema, contact dermatitis, urticaria, acne and spots. Contact dermatitis can arise from two mechanisms: primary irritation, through the action of irritant substances; or sensitization, in the presence of an allergenic ingredient (Birmingham, 1965).

Clinical studies to evaluate the irritation and sensitization potential of a product must consider a number of variables including the components used in the formulation, ingredient concentration, absorption, amount applied, skin condition, application directions and frequency, as well as the cumulative effect (Dooms-Goossens, 1993). The most common form of intolerance to cosmetics is characterized by irritation, burning sensation, redness, pruritus and erythema at the application site (Lumelsky *et al.*, 2001).

Skin is characterized as 'sensitive' if it commonly presents a non-inflammatory response to application of topical products, as realized through subjective sensations such as stinging, burning and itching, often without any visible signs or symptoms. The absence of visible signs or symptoms of irritation presents a challenge in the objective diagnosis of sensitive skin. However, several substances are known to trigger an irritant response in people with sensitive skin, such as benzoic acid, cinnamic acid, non-ionic emulsifiers, sodium lauryl sulfate, lactic acid, propylene glycol, urea and sorbic acid (De Groot *et al.*, 2010; Lundov *et al.*, 2010). Therefore, a routine test to clinically diagnose sensitive skin is a lactic acid sting test (LAST), whereby an aqueous solution of lactic acid is applied to the nasolabial fold to attempt to trigger a sensorial response, often alongside a placebo such as saline. The stinging sensation to the irritant may be measured in a binary way (i.e. presence or absence) or with a magnitude scale (Farage *et al.*, 2006). The LAST procedure allows for the clinical diagnosis and enrollment of subjects with sensitive skin into clinical trials to enable the local tolerance of an investigational product to be evaluated in this population.

2.1 Study Rationale

GSK CH has developed a new cosmetic facial serum intended to be suitable for use by adult consumers with sensitive facial skin. Clinical data are required to demonstrate that the developmental formulation has a favorable local tolerance profile in the target population under normal conditions of use, prior to commercialization.

Complete information for the developmental cosmetic facial serum and the comparator cosmetic facial serum may be found in the single reference safety document (SRSD), which for this study is the Safety Statement.

2.2 Background

A cosmetic product that is freely available to the consumer must be safe when applied under normal or reasonably foreseeable conditions of use. Thus, as a general requirement, the safety of a developmental formulation should be confirmed before it is marketed.

Acceptability 'in-use' studies are useful clinical models with which to determine the irritation potential (local tolerance) of a cosmetic formulation to provide confidence an investigational product is suitable for general sale in the target population. Such studies aim to provide a clinical and subjective characterisation of the signs and symptoms of irritation following regular application of a topical product and often involve dermatologist and ophthalmologist oversight.

The investigational product is a developmental formulation intended to be used as a cosmetic serum by healthy adult consumers with sensitive facial skin. The formulation has been designed to provide topical moisturization while minimizing the quantity of known irritants and allergens.

The objective of this clinical study is to determine the local cutaneous and ocular tolerance of a developmental facial serum product in healthy females with clinically confirmed sensitive facial skin under normal conditions of use.

2.3 Mechanism of Action/Indication

Cosmetic products are preparations applied to the body, especially the face, intended to be applied for cleansing, beautifying, promoting attractiveness, or altering the appearance without affecting the body's structure or functions. The investigational product is a cosmetic facial serum that is intended to be applied topically by healthy female subjects with sensitive skin, immediately after cleansing.

Serum is a skincare product applied directly to the skin after cleansing but before moisturizing with the intent of delivering ingredients directly onto the skin.

The European Union Cosmetics Directive defines a cosmetic as any substance or preparation intended to be placed in contact with the external parts of the human body with a view exclusively or mainly to cleaning, perfuming, changing appearance and/or correcting body odors and/or protecting or keeping in good condition (European Commission (EC), 2009).

3 STUDY OBJECTIVES AND ENDPOINTS

Table 3-1 Study Objectives and Endpoints

| Objective(s) | Endpoint(s) |
|---|---|
| Primary | |
| To determine the local cutaneous tolerance profile of the investigational product in healthy females with sensitive facial skin under normal conditions of use. | Change from baseline (prior to any product application) in dermatologist visual assessment scores of signs and symptoms of cutaneous irritation to 21 (+2) days of product use. |
| Secondary | |
| To determine the local ocular tolerance profile of the investigational product in healthy females with sensitive facial skin under normal conditions of use. | Change from baseline (prior to any product application) in ophthalmologist visual assessment scores of signs and symptoms of ocular irritation to 21 (+2) days of product use. |
| To determine the local cutaneous and ocular tolerance of the investigational | Change from baseline in subject self-assessment scores of signs and symptoms |

| | |
|---|--|
| product from the perspective of the subject in healthy females with sensitive facial skin under normal conditions of use. | of cutaneous and ocular irritation to 1-2 hours after first product application and following 21 (+2) days of use. |
| Safety | |
| To evaluate the general safety of two cosmetic facial serums. | Frequency and severity of Adverse Events. |

The objective of this clinical study is to determine the local tolerance profile of a developmental facial serum product in healthy females with sensitive facial skin under normal conditions of use, following 21 (+2) days twice daily application.

This study will be considered a success if at least 90% of completed subjects do not have a significant increase (i.e. a unit increase score of 1 in the total score) from baseline in dermatologist assessed signs and symptoms of cutaneous irritation following 21 (+2) days of investigational product use.

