4.4 End of Study Definition

A subject will be considered to have completed the study if they complete all phases of the study, including the last visit or the last scheduled procedure shown in the Schedule of Activities. The end of this study is defined as the date of the last subject's last visit.

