7 DISCONTINUATION OF STUDY INTERVENTION AND SUBJECT DISCONTINUATION/WITHDRAWAL

7.1 Subject Discontinuation/Withdrawal

A subject may withdraw from the study at any time at his or her own request, or may be withdrawn at any time at the discretion of the investigator or sponsor for safety, behavioral reasons, or the inability of the subject to comply with the protocol-required schedule of study visits or procedures.

The following circumstances require discontinuation of study product and/or premature subject withdrawal:

- Protocol violation that may impact the subject's safety
- Withdrawal of informed consent
- Subject lost to follow-up
- Unblinding of the subject
- Pregnancy

If a subject is discontinued or prematurely withdraws from the study, the reason(s) for discontinuation or withdrawal and the associated date must be documented in the relevant section(s) of the CRF.

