7.2 Lost to Follow up

A subject will be considered lost to follow up if he or she repeatedly fails to return for scheduled visits and is unable to be contacted by the study site.

If a subject fails to return to the site for a required study visit the site must attempt to contact the subject and reschedule the missed visit as soon as possible and counsel the subject on the importance of maintaining the assigned visit schedule and ascertain whether or not the subject wishes to and/or should continue in the study.

Final safety assessments should be carried out wherever possible when the subject returns to the study site, which will include the following:

- Dermatologist assessment of cutaneous irritation
- Ophthalmologist assessment of ocular irritation
- Subject self-assessment questions

Before a subject is deemed lost to follow up, the investigator or designee must make every effort to regain contact with the subject (where possible, 3 telephone calls and, if necessary, a certified letter to the subject's last known mailing address or local equivalent methods). These contact attempts should be documented. If contact is made with the subject, the investigator should inquire about the reason for withdrawal, request that the subject return all products that they had been dispensed and request that the subject return for a final visit, and follow-up with the subject regarding any unresolved adverse events (AEs), and follow-up assessments (dermatologist and ophthalmologist assessments and subject self-assessment questions).

Should the subject continue to be unreachable, he/she will be considered to have withdrawn from the study and lost to follow up.

Lack of completion of all or any of the early termination procedures will not be viewed as protocol deviations so long as the subject's safety was preserved.

If the subject withdraws from the study and also withdraws consent for disclosure of future information, no further evaluations should be performed and no additional data should be collected. The sponsor may retain and continue to use any data collected before such withdrawal of consent.

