8.1.11 Supervised Product Application

Sufficient product will be provided to last the complete study period. Subjects will use the product at home, twice a day during the study period of 21 (+ 2) days, including the morning of the final visit and will be instructed to contact the study site if they have any reactions.

Subjects will be dispensed a paper diary alongside their assigned product to be completed at home to record product use.

Spontaneous reporting of adverse events and those elicited by asking subjects to respond to a non-leading question such as "How do you feel?" will be assessed and any AEs recorded in the CRF.

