8.2.1 Dermatologist Assessment

A final assessment by the same dermatologist, will be completed at the end of the 21 (+2) day product use period (Visit 2).

The intensity of any visual signs of dermal irritation will be recorded according to the grade of the reactions according to the Dermatological Evaluation ([Safety and Other Assessments](#)). The dermatologist is responsible for grading the level of cutaneous irritation and their opinion on the correct classification of the irritation scores is final.

Any observed cutaneous response that can be denoted according to the grade of the reactions will not be considered an adverse event. Only in the case of unusual reactions, in the opinion of the qualified dermatologist, will these reactions and the consequences observed upon evaluation be documented as AE's.

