4.4 Analysis of Tolerability

4.4.1 Primary Tolerability Endpoint

4.4.1.1 Primary Tolerability Endpoint Definition

The primary endpoint will be the change from baseline (prior to any product application) in dermatologist signs and symptoms of cutaneous irritation total score following 21 (+2) days of product use.

This study will be considered a success if at least 90% of completed subjects do not have a significant increase (i.e. a unit increase score of 1 in the total score) from baseline in dermatologist assessed signs and symptoms of cutaneous irritation following 21 (+2) days of investigational product use.

Calculation of dermatologist assessment of signs and symptoms of cutaneous irritation total score and change from baseline in total score:

The cutaneous irritation total score will be calculated in the following way:

Cutaneous irritation total score = dermal response score of erythema + dermal response score of dryness + dermal response score of scaling + dermal response score of edema

Where, the dermal response score is described in [Table 4-1](#).

Table 4-1 Dermatological Evaluation

Attribute	Description (Score)				
Erythema	None (0)	Very Slight (0.5)	Slight (1)	Moderate (2)	Severe (3)
Dryness	None (0)	Very Slight (0.5)	Slight (1)	Moderate (2)	Severe (3)
Scaling	None (0)	Very Slight (0.5)	Slight (1)	Moderate (2)	Severe (3)
Edema	None (0)	Very Slight (0.5)	Slight (1)	Moderate (2)	Severe (3)

For example, if the dermal responses score of erythema = 2, dermal responses score of dryness = 0.5, dermal responses score of scaling = 1 and dermal responses score of edema = 0.5.

Then the cutaneous irritation total score will be:

$$\text{Total score} = 2 + 0.5 + 1 + 0.5 = 4.$$

Change from baseline in dermatologist signs and symptoms of cutaneous irritation total score = total score at day 21 – total score at baseline.

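### The 90% success rule counts completers only, so a subject who withdraws for irritation before Visit 2 drops out of it; the percentage reads too high if irritated subjects leave more often than others.

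*Protocol*

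**What the plan says.** Protocol 3 states the criterion: "This study will be considered a success if at least 90% of completed subjects do not have a significant increase", where a significant increase is a rise of one unit in the total score. SAP 4.4.1.1 repeats it, and neither document gives another denominator.

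Protocol 4.4 treats subjects as having completed "if they complete all phases of the study, including the last visit or the last scheduled procedure shown in the Schedule of Activities". SAP 4.4.1.1 fixes the time point: "Change from baseline in dermatologist signs and symptoms of cutaneous irritation total score = total score at day 21" minus the baseline total. The Schedule of Activities has one post-baseline dermatologist assessment, at Visit 2.

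Other provisions bear on early leavers:

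- Protocol 8.1.11 says that subjects "will be instructed to contact the study site if they have any reactions", and Protocol 1 adds that "The investigator may schedule visits (unplanned visits) in addition to those listed on the schedule of activities".
- Protocol 7.2 says "Final safety assessments should be carried out wherever possible when the subject returns to the study site", and the list includes the dermatologist assessment. The same section says that missed early-termination procedures are not deviations as long as safety was preserved.
- Protocol 12.2.6 runs the primary analysis on the Safety population. Protocol 12.2.10 and SAP 4.4.3 rule out imputation and include dropouts up to discontinuation.
- SAP 4.1.1 tabulates discontinuations by reason, and SAP 4.6.1 lists adverse events leading to discontinuation.

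SAP 4.4.1.2 adds a summary line for changes greater than 1.

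**The concern.** The endpoint is tolerance, so leaving the study because the product irritates is itself information about the outcome. A rule restricted to completers discards it. Every subject has lactic-acid-positive sensitive skin and may withdraw at any time, so such withdrawals are plausible. At stake is the study's one declared verdict: a product below the sponsor's own 90% bar could be called a success because some of those it irritated were not there to be scored on Day 21.

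**Working it through.** **1. Trace one subject.** She reacts on Day 8, contacts the site and withdraws.

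- She does not reach Visit 2, so under Protocol 4.4 she is not completed and the rule ignores her.
- If she is scored on exit, whether that score enters the primary table is unclear. The Safety population and the dropout wording point one way, and the Day 21 definition of change points the other. On either reading she stays outside the success rule.
- The disposition table may show her by reason. The adverse-event listing may not, because Protocol 5.8 and 9.2.1 say that a gradable reaction is not an adverse event. Neither output feeds the rule.

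**2. The plan's own figures.** No power, dropout rate or irritation rate is stated, so there is no calculation to reproduce. Randomizing 90 for 60 completers leaves room for 30/90 = 33.3% non-completers, with no reason attached. With 30 completers, the smallest count reaching 90% is 27.

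**3. Recount, 30 completers, k irritation withdrawals added as failures.**

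| Clear completers | k | Percentage |
|---|---|---|
| 27 | 0 | 27/30 = 90.0% |
| 27 | 1 | 27/31 = 87.1% |
| 27 | 2 | 27/32 = 84.4% |
| 30 | 3 | 30/33 = 90.9% |
| 30 | 4 | 30/34 = 88.2% |

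**4. Expected completer percentage.** Let p be the true share without a significant increase, s the withdrawal probability of irritated subjects and t that of others, all assumed. Expected value = p(1−t) / [p(1−t) + (1−p)(1−s)]. At p = 0.85:

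- s = 0.25, t = 0: 0.85/0.9625 = 88.3%
- s = 0.50, t = 0: 0.85/0.925 = 91.9%
- s = t = 0.25: 0.6375/0.75 = 85.0% (no bias)
- s = 0.10, t = 0.25: 0.6375/0.7725 = 82.5% (reads too low)

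**5. Chance that the rule passes.** Exact binomial calculation with 45 dosed (90 split 1:1, an assumption because the ratio is not stated) and t = 0. The rule passes if clear completers divided by completers is at least 0.90.

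| True p | s = 0 | s = 0.25 | s = 0.50 |
|---|---|---|---|
| 85% | 17.5% | 41.7% | 73.2% |
| 90% | 52.7% | 75.3% | 92.5% |
| 95% | 92.7% | 97.4% | 99.5% |

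At 85% the last two columns need few withdrawals: 45 × 0.15 × 0.25 = 1.7 and 45 × 0.15 × 0.50 = 3.4 expected.

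**6. What counting irritation withdrawals as failures costs.** Take 45 dosed, s = t = 0.25, no exit scores, and every irritated dropout recorded as such. Irritated dropouts return to the denominator but tolerant ones do not, so the expected figure is p(1−t) / [p(1−t) + (1−p)].

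| True p | Expected figure | Reaches 90% | Completer rule passes |
|---|---|---|---|
| 85% | 0.6375/0.7875 = 81.0% | 8.0% | 22.8% |
| 90% | 0.675/0.775 = 87.1% | 32.9% | 54.7% |
| 95% | 0.7125/0.7625 = 93.4% | 80.9% | 90.6% |

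**The case against.** **No bias is demonstrated.** A reader might infer that this trial's percentage will be inflated, or that the one-third allowance anticipates irritation dropouts. The documents support neither. They give no withdrawal rate by reason, and the direction depends on who leaves. This objection stands: the finding is conditional.

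**The model is upper-end.** It treats each irritation withdrawal as someone who would have failed on the dermatologist score. Protocol 2 says that sensitive skin often stings, burns or itches without visible signs, and those sensations are not on the scale in Protocol 9.2.1. A reaction may also have settled by Day 21. If the one withdrawal in step 3 would not have failed, the count is 28/31 = 90.3% and the rule is met. This stands too.

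**The withdrawals are not hidden.** A reader might infer that they vanish from the report. They do not: disposition by reason and per-subject score listings are planned, and the study is non-comparative without formal inference. That lowers the consequence, but the stated verdict still ignores these subjects.

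**Replacing the rule would bring its own bias.** Step 6 shows that, with equal dropout, a figure counting irritation withdrawals as failures can miss 90% for a product that truly meets it. That argues for showing it beside the completer rule and against substituting it.

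**Stopping the serum is not the same as withdrawing.** A reader might infer that anyone who stops the product is excluded. Protocol 7.1 separates the two: "The following circumstances require discontinuation of study product and/or premature subject withdrawal". The documents do not say whether a subject who stops but attends Visit 2 is a completer. If she is, the rule counts her.

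**Conclusion.** The point holds on the text. A subject who withdraws for irritation before Visit 2 is outside the success rule, with or without an exit score, and no other provision brings her in. The percentage reads too high only if irritated subjects withdraw more often than others.

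Near the bar, one or two such withdrawals can change the result. At a true 95% the effect is small: 92.7% to 99.5% across the scenarios. All rates, the 45 per arm, and the equation of irritation withdrawal with score failure are assumptions, and the last makes the sizes upper-end. The documents do not support concluding that the completer rule is wrong and must be discarded. They support reporting how far the verdict depends on it. This is a cheap improvement to a descriptive study.

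**What to change.** Keep the completer percentage. In SAP 4.4.1.1 and 4.4.1.2, pre-specify beside it, for investigational-product subjects in the Safety population:

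- **(a)** a percentage using the Day 21 dermatologist score or, if there is none, the early-termination score, and counting as failures those unscored withdrawals whose recorded reason is irritation or product intolerance;
- **(b)** a worst-case percentage with all missing scores as failures.

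State that a success conclusion which does not hold under (a) must be reported as sensitive to irritation withdrawals.

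The cost is a few table rows and possibly one withdrawal-reason category, so that irritation can be identified. Figure (a) can read low when tolerant subjects also drop out (step 6), which is why it should not replace the completer rule. Figure (b) is a bound: with 25% of everyone unscored and a true 90%, its expected value is 0.90 × 0.75 = 67.5%.

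Separately, reconcile the threshold. Protocol 3 and SAP 4.4.1.1 treat a rise of 1 as significant, while the added line in SAP 4.4.1.2 counts only changes above 1. That line misses a rise of exactly 1, such as erythema and dryness each going from 0.5 to 1.
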